Appendix 1: IPSS Score		
Symptom	Question	Score
Incomplete Emptying	Over the past month, how often have you had a sensation of not emptying your bladder completely after you finished urinating?	0: None
		1: Less than 1 time in 5
		2: Less than half the time
		3: About half the time
		4: More than half the time
		5: Almost always
Frequency	Over the past month, how often have you had to urinate again less than two hours after you finished urinating?	0: None
		1: Less than 1 time in 5
		2: Less than half the time
		3: About half the time
		4: More than half the time
		5: Almost always
Intermittency	Over the past month, how often have you found you stopped and started again several times when you urinated?	0: None
		1: Less than 1 time in 5
		2: Less than half the time
		3: About half the time
		4: More than half the time
		5: Almost always
Urgency	Over the past month, how difficult have you found it to postpone urination?	0: None
		1: Less than 1 time in 5
		2: Less than half the time
		3: About half the time
		4: More than half the time
		5: Almost always
Weak Stream	Over the past month, how often have you had a weak urinary stream?	0: None
		1: Less than 1 time in 5
		2: Less than half the time

		3: About half the time
		4: More than half the time
		5: Almost always
Straining	Over the past month, how often have you had to push or strain to begin urination?	0: None
		1: Less than 1 time in 5
		2: Less than half the time
		3: About half the time
		4: More than half the time
		5: Almost always
Nocturia	Over the past month, how many times did you typically get up at night to urinate?	0: None
		1: 1 time
		2: 2 times
		3: 3 times
		4: 4 times
		5: 5 or more times

1. Total Score Calculation: Sum the scores of the above 7 items. The total score ranges from 0 to 35.
 
①Mild symptoms: 0 - 7 ②Moderate symptoms: 8 - 19 ③Severe symptoms: 20 - 35
		

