6.1.2 Intervention

On the day following surgery (postoperative day 1) at 9:00 am, the nurse will perform the corresponding intervention operations for patients in both groups based on the group assignment indicated in the randomization envelope. Before the intervention, both groups of patients must complete the CRBD (Catheter-Related Bladder Discomfort) grading assessment by the assigned nurse (Appendix 3). During the patient's first catheterization, the use of selective α 1-adrenergic receptor blockers (such as tamsulosin) is not permitted.

1) The ICCAUT strategy included intermittent urethral catheter clamping and active urination training. In the ICCAUT group, intermittent catheter clamping was initiated at 9:00 am on the first postoperative day. In each cycle, the catheter was clamped for 3 h, followed by a 5-min release. The next cycle began as soon as the previous cycle had been completed. Catheter training concluded at 10:00 pm on the first postoperative day, and the catheter was left open during the night. The urinary catheter was removed on the second postoperative day, and the training did not stop until the catheter had been removed. During the training period, if the patient experienced a strong urge to urinate before the 3-h clamping time was over, the clamping could be released in advance for 5 min, allowing the patient to proceed to the next cycle of bladder training. Each time the catheter was released, the patients were encouraged to actively initiate urination to facilitate complete bladder emptying. We refer to this catheter management strategy, which involves intermittent clamping of the catheter and active urination during the release periods, as the ICCAUT

management strategy.

2) For patients in the free-draining group, no intervention was performed using a catheter during this period. The urinary catheter was removed at 9:00 am on the second postoperative day.

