3) Before the urinary catheter is removed on the second day, both groups of patients must complete the CRBD (Catheter-Related Bladder Discomfort) grading assessment again by the assigned nurse (Appendix 3), and urine samples must be collected for urinalysis and urine culture. Additionally, patients in the ICCAUT group must scan a code to fill out the Bladder Training Quality Self-Assessment Form (Appendix 4) before the catheter is first removed. After the catheter is removed, the time from the first catheter removal to the first urination, as well as the volume of the first urination, should be recorded for both groups of patients.

4) Immediately after the first urination, a bladder ultrasound must be performed to assess the residual urine volume in the bladder. The bladder ultrasound is conducted by a fixed radiologist from the ultrasound imaging department, who is exclusively assigned to our department and is located in the same therapeutic area as the patient. After the urinary catheter is removed, the patient must be observed and the situation of any secondary catheterization must be recorded. The observation period is the following 7 days after first urinary catheter removal. For patients who undergo secondary catheterization, the time from the first catheter removal to the secondary catheterization, the volume of urine drained after secondary catheterization, the method of secondary catheterization, and the reason for secondary catheterization must be recorded.

5) Record the IPSS score and ICIQ-SF score of the patient on the day following the first catheter removal (excluding patients who underwent secondary catheterization). Record complications within 30 days after surgery and their Clavien-Dindo classification (Appendix 5).

6.1.3 Discharge and follow-up.

After discharge, when the patient returns for a follow-up visit one month after

surgery, the physician must collect information on complications and their grading within the first postoperative month, and conduct an assessment using the one-month postoperative urinary function score form.

Table 1: Study Enrollment, Intervention, and Outcome Assessment Form

Item	Time point	Study phase		
		Surgery and Recruitment randomization		Post-randomization
		t	n	
Enrollment:				
Screen suitable population			X	
Informed consent			X	
Baseline and surgery-related data collection		X		X
Randomization			X	
Intervention:				
ICCAUT group				X
Free-drainage group				X
Assessment:				

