12.1 Case Report Form/Electronic Data Recording

The Case Report Form (CRF) includes the following primary outcome measures: incidence of urinary dysfunction, including bladder residual urine volume after the

first urination, rate of secondary catheterization, time from catheter removal to secondary catheterization (hours), method of secondary catheterization (suprapubic puncture/urethral catheterization), reasons for secondary catheterization, and urine volume drained after secondary catheterization (ml). Secondary outcome measures include: urinary tract infection status (white blood cell count in urine, bacterial content, and positive/negative urine culture before catheter removal), time to first urination after catheter removal (hours), bladder residual urine volume after the first urination (milliliters), CRBD grading assessment, bladder training quality self-assessment form for the bladder training group, postoperative complications within 30 days (incidence of complications, types of complications, and grading of complications), and urinary function assessment on the second day after catheter removal (ICIQ-SF, IPSS score). Other collected baseline indicators include: gender, age, underlying diseases and medical history (hypertension, diabetes, cardiovascular disease, cerebrovascular disease, history of pelvic surgery), history of benign prostatic hyperplasia in males (confirmed by medical history or imaging), preoperative IPSS score, preoperative ICIQ-SF score, preoperative radiotherapy and chemotherapy status, preoperative urine routine white blood cell count, preoperative urine routine bacterial count, preoperative urine culture results, ASA, BMI, preoperative imaging assessment results (preferably rectal MRI), including the distance from the lower edge of the tumor to the anal margin, the relationship between the lower edge of the tumor and the peritoneal reflection (above/below the peritoneal reflection), clinical T staging, clinical N staging, MRF status, EMVI status, surgery duration, surgical procedures, including low anterior resection (LAR), intersphincteric resection (ISR), abdominoperineal resection (APR), transanal TME (TaTME), Bacon surgery, stoma status (ileum/colon, single/double), surgical technique (robotic/laparoscopic), and postoperative pathological conditions (pathological T staging, pathological N staging, CRM, DRM). See the CRF form for details.

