Appendix 2: ICIQ-SF Score

International Consultation on Incontinence Questionnaire - Urinary Incontinence

Short Form (ICIQ-UI SF)

1. Please write in your date of birth: _____

2. Are you (check one): Female Male

3. How often do you leak urine? Check one box.

0 Never

1 About once a week or less often

2 Two or three times a week

3 About once a day

4 Several times a day

5 All the time

4. We would like to know how much urine you think leaks. How much urine do you usually leak (whether you wear protection or not)? Check one box.

0 None

2 A small amount

4 A moderate amount

6 A large amount

5. Overall, how much does leaking urine interfere with your everyday life? Please circle a number between 0 (not at all) and 10 (a great deal)

0 1 2 3 4 5 6 7 8 9 10

Not at all A great deal

ICIQ score: Sum scores 3 + 4 + 5

6. When does urine leak? Please check all that apply to you.

Never – urine does not leak

Leaks before you can get to the bathroom

Leaks when you cough or sneeze

Leaks when you are asleep

Leaks when you are physically active / exercising

Leaks when you have finished urinating and are dressed

- Leaks for no obvious reason
- Leaks all the time

The grading of urinary incontinence:

- Total score of 0 - 5: No urinary incontinence or mild urinary incontinence.
- Total score of 6 - 10: Moderate urinary incontinence.
- Total score of 11 and above: Severe urinary incontinence.

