6.4.1 Preoperative characteristics

- Sex, categorical variable: male, female;
- Age, continuous variable, measured in years;
- Body Mass Index, continuous variable, measured in kg/m²;
- American Society of Anesthesiologists grading, categorical variable: I, II, III, IV;
- Neoadjuvant radiotherapy/chemoradiotherapy, categorical variable: no, yes;
- Tumor site, categorical variable: the lower edge of the tumor is above the peritoneal reflection, the lower edge of the tumor is not above (below or at) the peritoneal reflection.
- The distance from the lower edge of the tumor to the anal margin, continuous variable, measured in centimeter;
- Benign prostatic hyperplasia, categorical variable: No, Yes;
- History of hypertension, categorical variable: No, Yes;
- History of diabetes, categorical variable: No, Yes;
- ICIQ-SF score at admission, continuous variable, measured in points;
- ICIQ-SF classification at admission, categorical variable: no or mild, moderate, severe;
- IPSS score at admission, continuous variable, measured in points;
- IPSS classification at admission, categorical variable: mild, moderate, severe;
- Clinical T stage, categorical variable: clinical complete response (cCR), T1, T2, T3, T4;
- Clinical N stage, categorical variable: N0, N1, N2;
- Clinical TNM stage, categorical variable: 0 stage, I stage, II stage, III stage, IV stage.

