6.5.3 Analysis of secondary endpoints

In the analysis of secondary endpoints, continuous variables will be described using the mean \pm standard deviation or the median (interquartile range); categorical variables will be described using counts (percentages). Missing values for secondary endpoints will neither be imputed nor subjected to sensitivity analysis.

Secondary endpoints:

Variables	Type	Effect size	P value
Urinary tract infection	categorical variable: no, yes	Absolute risk difference (95% CI)	*.***
The time from catheter removal to the first micturition	continuous variable: hours	Difference (95% CI) by Hodges-Lehmann method	*.***
Catheter-related bladder discomfort (CRBD)	categorical variable: level 0, level 1, level 2, level 3	Absolute risk difference (95% CI)	*.***
ICIQ-SF score on the second day after the first removal of the urinary catheter	continuous variable: points	Difference (95% CI) by Hodges-Lehmann method	*.***

ICIQ-SF classification on the second day after the first removal of the urinary catheter	categorical variable: no or mild, moderate, severe	Absolute risk difference (95% CI)	*.***
IPSS score on the second day after the first removal of the urinary catheter	continuous variable: points	Difference (95% CI) by Hodges-Lehmann method	*.***
IPSS classification on the second day after the first removal of the urinary catheter	categorical variable: mild, moderate, severe	Absolute risk difference (95% CI)	*.***
Surgical Complications within 30 days after surgery	categorical variable: no, yes	Absolute risk difference (95% CI)	*.***
Specific types of complications	categorical variable: no, yes	-	-
.....	-	-
Clavien - Dindo Classification of Surgical Complications \geq III	categorical variable: no, yes	Absolute risk difference (95% CI)	*.***
Bladder residual urine volume $>$ 200 ml after the first voiding	categorical variable: no, yes	Absolute risk difference (95% CI)	*.***

Other outcomes of interest:

- Self-assessment form on the quality of bladder training, presented in the form of a bar chart.
- Postoperative hospital stays, continuous variable, measures in days;
- Duration of urinary catheter indwelling, categorical variable: within 1 day, 2 days, \geq 3 days;
- Time from catheter removal to second catheterization, categorical variable: within 1 day, 2 days, \geq 3 days;
- Volume of first urination after surgery, continuous variable, measures in milliliters;

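### The only post-removal IPSS that the SAP analyses is taken one or two days after catheter removal on a form that asks about the past month, so it may dilute a true difference by an unknown amount; the admission score and the one-month IPSS, both collected, are left out of the comparison

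*Protocol*

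**What the plan says.** Secondary endpoint 4 (Protocol version 2.0, section 2.2.2; SAP 4.2) is urinary function after catheter removal, measured with the IPSS and the ICIQ-SF.

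- **Form.** Protocol Appendix 1 prints seven IPSS items, each with a past-month recall period. The first reads "Over the past month, how often have you had a sensation of not emptying your bladder completely after you finished urinating". Neither document tells patients to answer only for the time since removal.
- **Timing of removal.** Protocol 6.1.2 states for the free-drainage group: "The urinary catheter was removed at 9:00 am on the second postoperative day". Section 5 sets the same time for both groups.
- **Timing of the early score.** Protocol 6.1.2, item 5, says "Record the IPSS score and ICIQ-SF score of the patient on the day following the first catheter removal" and leaves out patients who were recatheterised. Protocol 12.1 places the assessment on the second day after removal, and SAP 6.5.3 lists "IPSS score on the second day after the first removal of the urinary catheter".
- **Analysis.** SAP 6.5.3 gives the effect size for the score as "Difference (95% CI) by Hodges-Lehmann method", and compares severity classes by absolute risk difference. SAP 6.1 allows a t-test or a Mann-Whitney test for continuous data. None of these uses a baseline value.
- **Admission score.** The same form is completed at admission (Protocol 6.1.1). SAP 6.4.1 lists "IPSS score at admission, continuous variable, measured in points" as a baseline characteristic, and SAP 6.5.1 uses its class as a candidate predictor of the primary endpoint. It plays no part in the IPSS comparison.
- **One-month score.** Protocol 6.1.3 and 6.2 collect the IPSS and ICIQ-SF one month after surgery. SAP 6.5.3 does not list them.

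**The concern.** The endpoint is meant to describe voiding after the catheter comes out. A form with a one-month window, completed one or two days after removal, asks mainly about the weeks before surgery. Randomisation takes place on the morning after surgery, so allocation cannot affect that period. To the extent that patients follow the printed wording, a true difference in post-removal symptoms shrinks in the score. A null result could then mean either that the strategy has no effect on symptoms or that the form asked about the wrong period, and the data would not separate the two.

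The unused admission score is a second, smaller matter. Stable preoperative differences between patients stay in the outcome as noise, although the plan already collects what is needed to remove part of it.

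**Working it through.** **Inputs.** Recall window of one month, taken as 28-31 days (Protocol Appendix 1). Surgery on day 0 and removal on day 2 (Protocol 6.1.2). Early score 1 day after removal (Protocol 6.1.2) or 2 days after (Protocol 12.1, SAP 6.5.3), so day 3 or day 4. One-month score taken as day 30 (Protocol 6.1.3, 6.2). The documents give no SD, expected difference or power for the IPSS.

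**The plan's own figure.** The only design figure is 180 per group for the primary endpoint. With 44.7% against 59.3%, two-sided 0.05 and 80% power, the unpooled formula gives (1.960 + 0.842)² × (0.447 × 0.553 + 0.593 × 0.407) / 0.146² = 180. It reproduces. It does not bear on the IPSS except as a group size for step 3.

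**Step 1: make-up of the recall window for the early score.** Share after removal = days since removal / window. About 2 days are surgery and catheter time; the rest precedes surgery.

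| Window | After removal, 1 day | After removal, 2 days | Before surgery, 1 day | Before surgery, 2 days |
|---|---|---|---|---|
| 28 days | 1/28 = 3.6% | 2/28 = 7.1% | 25/28 = 89.3% | 24/28 = 85.7% |
| 30 days | 1/30 = 3.3% | 2/30 = 6.7% | 27/30 = 90.0% | 26/30 = 86.7% |
| 31 days | 1/31 = 3.2% | 2/31 = 6.5% | 28/31 = 90.3% | 27/31 = 87.1% |

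**Step 2: the one-month score.** (30 - 2)/30 = 28/30 = 93% of the window follows removal.

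**Step 3: what dilution could do (illustration only).** Let w be the weight that an answer gives to symptoms since removal. The expected difference in scores is then w × δ. Assume δ = 3 points, SD = 6 and 180 per group; none of the IPSS values comes from the documents. The standard error is 6 × √(2/180) = 0.632. Power, counting significance in the right direction only, is Φ(wδ/0.632 - 1.96).

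- w = 1 (current symptoms only): Φ(4.743 - 1.96) = 99.7%
- w = 0.5: Φ(2.372 - 1.96) = 66%
- w = 2/30 (difference 0.2): Φ(0.316 - 1.96) = 5.0%
- w = 1/30 (difference 0.1): Φ(0.158 - 1.96) = 3.6%

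With no effect at all this calculation returns 2.5%. Over SD 4-8, δ 2-4 and 150-200 per group, the last two cases span 3-10%, against 58% to over 99% undiluted.

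**Step 4: what baseline adjustment can and cannot do.** Adjusting for the admission score multiplies the variance by 1 - r², where r is the correlation between admission and early scores (assumed).

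| r | 1 - r² | Power, w = 0.5 (66% unadjusted) | Power, w = 2/30 (5.0% unadjusted) |
|---|---|---|---|
| 0.3 | 0.91 | 70% | 5.2% |
| 0.5 | 0.75 | 78% | 5.5% |
| 0.7 | 0.51 | 91% | 6.5% |

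Adjustment sharpens whatever difference reaches the score. It does not restore a difference that the recall window has removed.

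**The case against.** The best case for the plan is that nothing in the documents shows how patients answer. Someone who has just had a catheter removed may well report how voiding feels now, whatever the form says. The 3-7% share assumes literal recall with every day weighted equally. This stands, and it makes that share an extreme rather than an estimate. It does not clear the plan: the endpoint's label does not reach the patient, the printed question does, and the reading is left to each respondent.

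Four stronger readings are tempting, and the documents do not support them.

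- *The early score mostly re-measures preoperative symptoms.* This holds only under literal recall. With half the weight on current symptoms, the illustration above keeps 66% power.
- *The ICIQ-SF has the same defect.* Appendix 2 as printed gives no recall period and asks in the present tense. Two of its six frequency options, such as "About once a week or less often", fit poorly after one or two days, but the other four and the amount and interference items can be answered. The recall argument is confined to the IPSS.
- *Leaving out the admission score biases the comparison.* Randomised groups compared on a follow-up score give an unbiased contrast. Chance imbalance is covered by the confidence interval and would show in the baseline table.
- *The form should be reworded now.* With 362 of 400 enrolled at the SAP date, a new heading could reach at most 38 patients (9.5%). It would mix two versions within one endpoint and break the match with the admission form.

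The scope is also limited. This is one of six secondary endpoints, the named secondary objective is urinary tract infection, and neither document says that a null early IPSS will be reported as no effect.

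**Conclusion.** The mismatch is real and can be verified from the form and the schedule: a one-month recall period, scored one or two days after removal, with no instruction to narrow it. Under literal recall about 3-7% of the window follows removal and 86-90% precedes surgery. How far a true difference is actually diluted lies between none and that extreme, and the plan offers no way to tell where. The omitted admission score costs precision by a factor that depends on an r the documents do not give; it is not the source of the dilution.

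The gap in the SAP is more telling than the early score itself. A one-month IPSS, for which the printed wording fits (about 93% of the window after removal), is already collected and is not tabulated. The primary endpoint, which rests on ultrasound residual volume and recatheterisation, is untouched. The shares assume removal on day 2 as planned; the power figures rest on assumed IPSS values and show direction, not size.

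**What to change.** 1. In SAP 6.5.3, compare the post-removal IPSS and ICIQ-SF scores adjusted for the admission score, by ANCOVA or rank-based ANCOVA, and describe this as a gain in precision only. The Hodges-Lehmann difference can stay as a supporting result.
2. Add the one-month IPSS, adjusted for the admission score, to the SAP table, and state that it was added in a SAP revision.
3. State in the SAP that a null early IPSS result under the one-month wording is not evidence of no effect on post-removal function.
4. Reconcile the assessment day between Protocol 6.1.2 (the day following removal) and Protocol 12.1 with SAP 6.5.3 (the second day). If the removal day counts as day one, the passages may mean the same day; say so if that is the case.

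Leave the form as it is for the remaining patients.

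The cost is SAP wording, one further tabulated outcome and a correction to one protocol passage. No new data are needed. The analysis waits for the last one-month visit, so the text can be settled before it starts. The one-month score answers a somewhat different question, recovery over the first month rather than function just after removal, and should be labelled so.

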Appendix 2: ICIQ-SF Score

International Consultation on Incontinence Questionnaire - Urinary Incontinence

Short Form (ICIQ-UI SF)

1. Please write in your date of birth: _____

2. Are you (check one): Female Male

3. How often do you leak urine? Check one box.

0 Never

1 About once a week or less often

2 Two or three times a week

3 About once a day

4 Several times a day

5 All the time

4. We would like to know how much urine you think leaks. How much urine do you usually leak (whether you wear protection or not)? Check one box.

0 None

2 A small amount

4 A moderate amount

6 A large amount

5. Overall, how much does leaking urine interfere with your everyday life? Please circle a number between 0 (not at all) and 10 (a great deal)

0 1 2 3 4 5 6 7 8 9 10

Not at all A great deal

ICIQ score: Sum scores 3 + 4 + 5

6. When does urine leak? Please check all that apply to you.

Never – urine does not leak

Leaks before you can get to the bathroom

Leaks when you cough or sneeze

Leaks when you are asleep

Leaks when you are physically active / exercising

Leaks when you have finished urinating and are dressed

- Leaks for no obvious reason
- Leaks all the time

The grading of urinary incontinence:

- Total score of 0 - 5: No urinary incontinence or mild urinary incontinence.
- Total score of 6 - 10: Moderate urinary incontinence.
- Total score of 11 and above: Severe urinary incontinence.

